Appendix 13: Study Details Specific to Atezo + Tira Arm

A13–5 ASSESSMENT OF SAFETY FOR ATEZO + TIRA ARM

A13–5.1 SAFETY PLAN FOR ATEZO + TIRA ARM

The safety plan for patients in this study is based on clinical experience with atezolizumab and tiragolumab in completed and ongoing studies. The anticipated important safety risks are outlined below (see Sections [A13–5.1.1](#), [A13–5.1.2](#), and [A13–5.1.3](#)). Guidelines for management of patients who experience specific adverse events are provided in Section [A13–5.1.4](#) and [Appendix 9](#).

Measures will be taken to ensure the safety of patients participating in this study, including the use of stringent inclusion and exclusion criteria and close monitoring of patients during the study. Because of the potential for overlapping toxicities for atezolizumab and tiragolumab, special caution will be taken by performing a planned safety evaluation phase for patients randomized to this arm (see Section [3.1.3](#)).

Administration of atezolizumab and tiragolumab will be performed in a monitored setting in which there is immediate access to trained personnel and adequate equipment and medicine to manage potentially serious reactions. Adverse events will be reported as described in Sections [5.2–5.6](#).

A13–5.1.1 Risks Associated with Atezolizumab

Atezolizumab has been associated with risks such as the following: IRRs and immune-mediated hepatitis, pneumonitis, colitis, pancreatitis, diabetes mellitus, hypothyroidism, hyperthyroidism, adrenal insufficiency, hypophysitis, Guillain-Barré syndrome, myasthenic syndrome or myasthenia gravis, facial paresis, myelitis, meningoencephalitis, myocarditis, pericardial disorders, nephritis, myositis, and severe cutaneous adverse reactions (SCARs). In addition, immune-mediated reactions may involve any organ system and lead to HLH. Refer to [Appendix 9](#) of the protocol and Section 6 of the Atezolizumab Investigator's Brochure for a detailed description of anticipated safety risks for atezolizumab.

A13–5.1.2 Risks Associated with Tiragolumab

Infusion-related reactions and immune-mediated hepatitis are identified risks of tiragolumab. Lymphopenia is a potential risk with tiragolumab. Although clinical evaluation of tiragolumab is limited and not all risks are known, as an antagonist of TIGIT, tiragolumab is anticipated to enhance T-cell and NK-cell proliferation, survival, and function. Therefore, tiragolumab may increase the risk of autoimmune inflammation (also described as immune-mediated adverse events).

Refer to [Appendix 9](#) of the protocol and Section 6 of the Tiragolumab Investigator's Brochure for a detailed description of anticipated safety risks of tiragolumab.

Appendix 13: Study Details Specific to Atezo + Tira Arm

A13–5.1.2.1 Infusion-Related Reactions

Because tiragolumab is a therapeutic monoclonal antibody and targets immune cells, IRRs associated with hypersensitivity reactions and/or target-mediated cytokine-release may occur. Clinical signs and symptoms of such reactions may include rigors, chills, wheezing, pruritus, flushing, rash, hypotension, hypoxemia, and fever.

IRRs have been reported in patients treated with tiragolumab, with or without atezolizumab. The majority of events were mild to moderate and manageable.

To minimize the risk and sequelae of IRRs, the initial dose of tiragolumab will be administered over 60 minutes followed by a 60-minute observation period. Subsequent infusions and observation times may be shortened if the preceding infusion was well tolerated. All infusions will be administered in an appropriate medical setting.

Refer to Section [A13–4.1.2](#) for detailed guidance on administration of tiragolumab in this study. Please see [Appendix 8](#) for guidance on anaphylaxis precautions and [Table A13–5](#) for guidance on the management of IRRs.

A13–5.1.2.2 Immune-Mediated Hepatitis

The use of tiragolumab to block the immune inhibitory receptor TIGIT serves to increase a baseline T-cell and NK-cell immune response, especially in combination with other checkpoint inhibitors (i.e., atezolizumab). A disruption in the functioning of immune checkpoint molecules may lead to imbalances in immunologic tolerance that results in an unchecked immune response, including immune-mediated hepatitis.

Refer to [Appendix 9](#) for guidance on the management of immune-mediated hepatitis.

A13–5.1.2.3 Immune-Mediated Adverse Events

Nonclinical models have suggested a role of TIGIT signaling interruption in autoimmunity. In a knockout model (TIGIT^{–/–}), loss of TIGIT signaling resulted in hyperproliferative T-cell responses and exacerbation of experimental autoimmune encephalitis (EAE). TIGIT^{–/–} and wild-type B6 mice were immunized with myelin oligodendrocyte glycoprotein peptide in an EAE using suboptimal doses. In contrast to the wild-type B6 mice, the majority of the TIGIT^{–/–} mice developed severe EAE (Joller et al. 2011).

Clinical experience with therapeutics intended to enhance anti-tumor T-cell responses has demonstrated that development of autoimmune inflammatory conditions is a general risk and may therefore be considered a potential risk of tiragolumab. Such immune-mediated adverse events have been described for virtually all organ systems and include, but are not limited to, colitis, pneumonitis, endocrinopathies, ocular toxicity,

Appendix 13: Study Details Specific to Atezo + Tira Arm

pancreatic toxicity, neurologic toxicity, cardiac toxicity, nephritis, myositis, and severe cutaneous adverse reactions.

Patients with a history of autoimmune disease will be excluded from this study (see Section 4.1.2).

In this study, immune-mediated adverse events will be considered adverse events of special interest and will be captured accordingly (see Section A13–5.2 for the list of adverse events of special interest and Section 5.4.2 for reporting instructions).

Suggested management guidelines for individual suspected immune-mediated adverse events are provided in Appendix 9.

A13–5.1.2.4 Lymphopenia

The IgG1 backbone of tiragolumab with intact Fc-effector function may lead to ADCC-mediated reduction in lymphocyte count. Lymphopenia is a potential risk with tiragolumab. Transient decreases in lymphocyte count without clinical sequelae have been observed in patients treated with tiragolumab, with or without atezolizumab.

Patients with a lymphocyte count $<0.5 \times 10^9/L$ (500/ μ L) will be excluded from the study (see Section 4.1.1), and complete blood counts will be monitored regularly during the study (see Appendix A13–6).

A13–5.1.2.5 Embryofetal Toxicity

Embryofetal toxicity is a potential risk with tiragolumab. Administration of tiragolumab is expected to have adverse effects on pregnancy based on the expression of TIGIT on decidual NK and CD8+ T cells (Powell et al. 2017; van der Zwan et al. 2018; Vento-Tormo et al. 2018), and the expected role of these cells in the recognition and response to foreign fetal, placental, and viral antigens at the maternal-fetal interface as well as maintenance of maternal-fetal tolerance. No reproductive or teratogenicity studies in animals have been conducted with tiragolumab. There are no clinical studies of tiragolumab in pregnant women. Tiragolumab should not be administered to pregnant women.

Refer to Section 6 of the Tiragolumab Investigator’s Brochure for a detailed description of embryofetal toxicity.

A13–5.1.3 Risks Associated with Combination Use of Atezolizumab and Tiragolumab

Based on results from clinical data with tiragolumab and atezolizumab, there are known and potential overlapping toxicities in patients treated with tiragolumab plus atezolizumab. Because the expected pharmacologic activity of these two molecules is

Appendix 13: Study Details Specific to Atezo + Tira Arm

to increase adaptive T-cell immune responses, there is the possibility of heightened immune responses.

Refer to Section 6 of the Tiragolumab Investigator's Brochure for a list of identified risks associated with tiragolumab in combination with atezolizumab. Based on the mechanism of action of tiragolumab and atezolizumab, additional immune-mediated adverse events are potential overlapping toxicities associated with combination use of tiragolumab plus atezolizumab.

Based on clinical experience to date, it is anticipated that immune-mediated adverse events following treatment with tiragolumab and atezolizumab will be amenable to monitoring and manageable in the setting of this combination study. The extensive experience with immune CPIs to date has been incorporated into the design and safety management plan (see Section 5.1) in order to reduce the potential risks to participating patients. Patients with a history of autoimmune disease will be excluded from this study (see Section 4.1.2). Patients previously treated with approved or experimental CIT will also be excluded from participation in Cohort 1. Owing to the risks of active viral infection and viral reactivation, patients with active infection (including, but not limited to, HIV, HBV, HCV, EBV, known and/or suspected chronic active EBV infection, or tuberculosis) and/or patients with recent severe infections will be excluded from this study (see Sections 4.1.1 and 4.1.2).

A13–5.1.4 Management of Patients Who Experience Specific Adverse Events in the Atezo + Tira Arm

A13–5.1.4.1 Dose Modifications

There will be no dose modifications for atezolizumab or tiragolumab in this study.

A13–5.1.4.2 Treatment Interruption for Toxicities

Atezolizumab and tiragolumab treatment may be temporarily suspended in patients experiencing toxicity considered to be related to study treatment. If corticosteroids are initiated for treatment of the toxicity, they must be tapered over ≥ 1 month to the equivalent of ≤ 10 mg/day oral prednisone before study treatment can be resumed, if warranted. In the neoadjuvant setting, the study treatment is limited to a pre-surgery window of 6 weeks. Treatment during this period should not be interrupted, unless a patient experiences toxicity. If toxicity meets criteria for interrupting/withholding atezolizumab and/or tiragolumab, atezolizumab and tiragolumab should be interrupted/withheld. After resolution of the toxicity, subsequent treatment cycles should only be considered if the benefit/risk profile is acceptable and if the surgery can be conducted within 2 weeks of the planned date. Otherwise, subsequent treatment cycles should be omitted to allow the patient to proceed directly to surgery without further delay.

Appendix 13: Study Details Specific to Atezo + Tira Arm

On the basis of the available characterization of mechanism of action, tiragolumab may cause adverse events similar to, but independent of, atezolizumab. Tiragolumab may also exacerbate the frequency or severity of atezolizumab-related adverse events or may have non-overlapping toxicities with atezolizumab. Because these scenarios may not be distinguishable from each other in the clinical setting, adverse events should generally be attributed to both agents, and dose interruptions or treatment discontinuation in response to adverse events should be applied to both tiragolumab and atezolizumab. If atezolizumab is withheld or discontinued, tiragolumab should also be withheld or discontinued. If tiragolumab is withheld or discontinued, atezolizumab should also be withheld or discontinued.

A13–5.1.5 Management Guidelines for Adverse Events

Guidelines for the management of patients who experience specific adverse events are provided in [Table A13-4](#), [Table A13-5](#), and [Appendix 9](#).

For cases in which management guidelines are not covered in [Appendix 9](#), patients should be managed and treatments should be withheld or discontinued as deemed appropriate by the investigator according to best medical judgment.

Table A13-4 Guidelines for Management of Patients Who Experience Adverse Events in the Atezo + Tira Arm

Event	Action to Be Taken
IRRs, anaphylaxis, and hypersensitivity reactions	
Guidelines for management of IRRs are provided in Table A13-5.For anaphylaxis precautions, see Appendix 8.For severe hypersensitivity reactions, permanently discontinue the causative agent.
Pulmonary, hepatic, GI, endocrine, ocular, immune-mediated myocarditis, CRS, pancreatic, dermatologic, neurologic, immune-mediated meningoencephalitis, renal, and systemic immune activation	
Guidelines for management of these events are provided in Appendix 9.

CRS = cytokine-release syndrome; GI = gastrointestinal; IRR = infusion-related reaction.

Appendix 13: Study Details Specific to Atezo + Tira Arm

A13–5.1.5.1 Infusion-Related Reactions

No premedication is indicated for the administration of the Day 1, Cycle 1 infusion of tiragolumab or atezolizumab. However, patients who experience an IRR with the Day 1, Cycle 1 infusion of tiragolumab or atezolizumab may receive premedication with antihistamines, antipyretic medication, or analgesics (e.g., acetaminophen) for subsequent infusions. Metamizole (dipyrone) is prohibited in treating atezolizumab-associated IRRs because of its potential for causing agranulocytosis.

IRRs are known to occur with the administration of monoclonal antibodies and have been reported with tiragolumab and atezolizumab. These reactions, which are thought to be due to release of cytokines and/or other chemical mediators, occur within 24 hours of tiragolumab or atezolizumab administration and are generally mild to moderate in severity. Guidelines for medical management of IRRs during Cycle 1 are provided in [Table A13-5](#). For subsequent cycles, IRRs should be managed according to institutional guidelines.

Table A13-5 Management Guidelines for Infusion-Related Reactions

Event	Management
IRR, Grade 1	
Reduce infusion rate to half the rate being given at the time of event onset.After the event has resolved, the investigator should wait for 30 minutes while delivering the infusion at the reduced rate.If the infusion is tolerated at the reduced rate for 30 minutes after symptoms have resolved, the infusion rate may be increased to the original rate.
IRR, Grade 2	
Interrupt infusion.Administer aggressive symptomatic treatment (e.g., oral or IV antihistamine, antipyretic medication, glucocorticoids, epinephrine, bronchodilators, oxygen, IV fluids).After symptoms have resolved to baseline, resume infusion at half the rate being given at the time of event onset.For subsequent infusions, consider administration of oral premedication with antihistamines, antipyretic medications, and/or analgesics and monitor closely for IRRs.
IRR, Grade 3 or 4	
Stop infusion.Administer aggressive symptomatic treatment (e.g., oral or IV antihistamine, antipyretic medication, glucocorticoids, epinephrine, bronchodilators, oxygen, IV fluids).Permanently discontinue tiragolumab and atezolizumab and contact the Medical Monitor.^a

IRR=infusion-related reaction.

^a If a study drug warrants permanent discontinuation, there should be no re-challenge of the drug. For combination regimens, both study drugs should be discontinued.

Appendix 13: Study Details Specific to Atezo + Tira Arm

A13–5.2 ADVERSE EVENTS OF SPECIAL INTEREST FOR THE ATEZO + TIRA ARM (IMMEDIATELY REPORTABLE TO THE SPONSOR)

Adverse events of special interest are required to be reported by the investigator to the Sponsor immediately (i.e., no more than 24 hours after learning of the event; see Section 5.2.3 for reporting instructions). Adverse events of special interest for the Atezo + Tira arm are as follows:

- Cases of potential drug-induced liver injury that include an elevated ALT or AST in combination with either elevated bilirubin or clinical jaundice, as defined by Hy's Law (see Section 5.3.5.7)
- Suspected transmission of an infectious agent by the study treatment, as defined below:

Any organism, virus, or infectious particle (e.g., prion protein transmitting transmissible spongiform encephalopathy), pathogenic or non-pathogenic, is considered an infectious agent. A transmission of an infectious agent may be suspected from clinical symptoms or laboratory findings that indicate an infection in a patient exposed to a medicinal product. This term applies only when a contamination of study treatment is suspected.

- Pneumonitis
- Colitis
- Endocrinopathies: diabetes mellitus, pancreatitis, adrenal insufficiency, hyperthyroidism, and hypophysitis
- Hepatitis, including AST or ALT $> 10 \times$ upper limit of normal
- Systemic lupus erythematosus
- Neurological disorders: Guillain-Barré syndrome, myasthenic syndrome or myasthenia gravis, and meningoencephalitis
- Events suggestive of hypersensitivity, IRRs, cytokine-release syndrome, influenza-like illness, HLH, and MAS
- Nephritis
- Ocular toxicities (e.g., uveitis, retinitis, and optic neuritis)
- Myositis
- Myopathies, including rhabdomyolysis
- Grade ≥ 2 cardiac disorders (e.g., atrial fibrillation, myocarditis, pericarditis)
- Vasculitis
- Autoimmune hemolytic anemia
- Severe cutaneous reactions (e.g., Stevens-Johnson syndrome, dermatitis bullous, toxic epidermal necrolysis)

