Appendix 13: Study Details Specific to Atezo + Tira Arm

Prolonged stable disease was observed in patients in the Phase Ia portion of the study at tiragolumab doses beginning at 400 mg. In the Phase Ib portion of the study with tiragolumab plus atezolizumab, the MTD was not reached. Anti-tumor activity, as measured by radiographic partial responses, was observed across doses for tiragolumab beginning at 30 mg and ranging up to 600 mg in combination with 1200 mg atezolizumab.

Refer to the Tiragolumab Investigator's Brochure for additional details.

A13-4 MATERIALS AND METHODS SPECIFIC TO ATEZO + TIRA ARM

A13-4.1 TREATMENT IN ATEZO + TIRA ARM

A13-4.1.1 Formulation, Packaging, and Handling

A13-4.1.1.1 Atezolizumab

The atezolizumab drug product will be supplied by the Sponsor as a 60 mg/mL concentrate for solution for infusion.

For information on the formulation, packaging, and handling of atezolizumab, refer to the pharmacy manual and the Atezolizumab Investigator's Brochure.

A13-4.1.1.2 Tiragolumab

The tiragolumab drug product will be supplied by the Sponsor as a 60 mg/mL concentrate for solution for infusion.

For information on the formulation, packaging, and handling of tiragolumab, refer to the pharmacy manual and the Tiragolumab Investigator's Brochure.

A13-4.1.2 Dosage, Administration, and Compliance

Patients in the atezolizumab plus tiragolumab (Atezo + Tira) arm will receive treatment for 2 cycles (6 weeks) as outlined in [Table A13-1](#) until surgery, or until unacceptable toxicity or loss of clinical benefit, whichever occurs first (see Section [3.1.2](#) for details). It is recommended that treatment be initiated no later than 7 days after randomization.

Table A13-1 Treatment Regimen for Atezo + Tira Arm

Cycle Length	Dose, Route, and Regimen (drugs listed in order of administration)
21 days	
• Atezolizumab 1200 mg IV on Day 1 of each cycle• Tiragolumab 600 mg IV on Day 1 of each cycle

Atezo = atezolizumab; Tira = tiragolumab.

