Appendix 13: Study Details Specific to Atezo + Tira Arm

TABLE A13-6 SCHEDULE OF ACTIVITIES FOR ATEZO+TIRA ARM (cont.)

Assessment/ Procedure ^a	Protocol Section	Screening (see Appendix 10)	Treatment Cycles (21-Day Cycles)		Pre-Surgery	Surgery CLND	Post-Surgery	Treatment Comp./ Discon. ^b	Long- Term Follow- Up	Surgery Follow-Up ^c
			Cycle 1	Cycle 2						
		D –28 to D –1	D1 (≤7D after randomization)	D1 (+ 1D)	Wk 6 (≤8D to surgery)	Wk 7 (± 7D)	Wk 10 (≥20D after surgery)	Wk 13	Every 3M (±7D)	6M after surgery (±7D)
Local Laboratory Assessments										
Hematology	4.5.9.1		x ^h	x ^h	x		x	x		x
Chemistry			x ^h	x ^h	x ⁱ		x	x		x
Lipid panel					x			x		
Coagulation (INR and aPTT)			x ^h	x ^h	x					
TSH, free T3 (or total T3), free T4			x ^h		x		x	x		x
Cardiac enzymes			x ^h	x ^h	x ^j			x		
C-reactive protein			x ^h	x ^h	x		x	x		x
Pregnancy test			x ^h	x ^h	x		x	x		x ^k
Urinalysis			Perform as clinically indicated.					x		
Central Laboratory Assessments										
Serum autoantibody sample	4.5.9.2		Perform if a patient experiences a suspected immune-mediated adverse event. Autoantibody analysis should be repeated for patients who develop signs or symptoms suggestive of autoimmune disease (e.g., lupus erythematosus).							
PK samples			Refer to Section A13-7.							
ADA samples			Refer to Section A13-7.							

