Appendix 13: Study Details Specific to Atezo + Tira Arm

TABLE A13-6 SCHEDULE OF ACTIVITIES FOR ATEZO+TIRA ARM (cont.)

- ^a If a visit is precluded because of a holiday, vacation, or other circumstance, it can occur outside of the specified window.
- ^b Regardless of whether they complete the study drug treatment period or discontinue study drug prematurely, patients who proceed to surgery will return to the clinic for a treatment completion/discontinuation visit 6 weeks after surgery and patients who do not proceed to surgery will return to the clinic for a treatment completion/discontinuation visit not more than 30 days after the final dose of study treatment.
- ^c Patients who proceed to surgery will have the surgery follow-up 6 months after surgery.
- ^d *Assessment may be performed within 24 hours prior to dosing during the treatment period.*
- ^e The disease status assessments at Week 13 should include a mandatory CT scan.
- ^f After initiation of study treatment, all adverse events will be reported until 30 days after the final dose of study treatment or until initiation of new systemic anti-cancer therapy, whichever occurs first, and serious adverse events and adverse events of special interest will continue to be reported until 135 days after the final dose of study treatment or until initiation of new systemic anti-cancer therapy, whichever occurs first. After this period, all deaths, regardless of cause, should be reported. In addition, the Sponsor should be notified if the investigator becomes aware of any serious adverse event that is believed to be related to prior exposure to study treatment (see Section 5.6). *For details on reporting all treatment-related non-serious adverse events that lead to surgical delay, see Section 5.6.* The investigator should follow each adverse event until the event has resolved to baseline grade or better, the event is assessed as stable by the investigator, the patient is lost to follow-up, or the patient withdraws consent. Every effort should be made to follow all serious adverse events considered to be related to study treatment or trial-related procedures until a final outcome can be reported.

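### The AESI lists of the three tiragolumab arms name hyperthyroidism but not hypothyroidism, so applying the list drops non-serious hypothyroidism first arising after the 30-day cut-off in Cohort 1 surgical patients

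*Combined protocol and SAP*

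**What the plan says.** **The lists.** Sections A13-5.2 (Atezo + Tira), A14-5.2 (RO7247669 2100 mg + Tira) and A16-5.2 (RO7247669 600 mg + Tira) carry the same endocrine entry: "Endocrinopathies: diabetes mellitus, pancreatitis, adrenal insufficiency, hyperthyroidism, and hypophysitis". The ocular, cardiac and cutaneous entries in these lists give examples. The endocrine entry is worded as complete.

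**The general statement.** A13-5.1.2.3 says: "In this study, immune-mediated adverse events will be considered adverse events of special interest and will be captured accordingly". A14-5.1.2.3 and A16-5.1.2.3 say the same, and each refers back to its own list. A14-5.1.1.3 and A16-5.1.1.3, the RO7247669 risk sections, are narrower: there only specified immune-mediated events are AESIs.

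**The named risk.** A13-5.1.1 lists, among the immune-mediated risks of atezolizumab, "diabetes mellitus, hypothyroidism, hyperthyroidism, adrenal insufficiency, hypophysitis".

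**The reporting windows.** Footnote f of Tables A13-6, A14-5 and A16-5 says that "all adverse events will be reported until 30 days after the final dose of study treatment or until initiation of new systemic anti-cancer therapy", whichever is first. It adds that serious adverse events and "adverse events of special interest will continue to be reported until 135 days after the final dose of study treatment", with the same early stop. The adverse event cells at Week 10 and Week 13 carry this footnote.

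**The tests.** The row "TSH, free T3 (or total T3), free T4" is scheduled in all three Cohort 1 tables at Cycle 1, Week 6 (pre-surgery), Week 10, Week 13 and 6 months after surgery.

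**The concern.** Hypothyroidism and hyperthyroidism are read from the same blood test, but only one of them is on the list. Once ordinary reporting closes, the list decides whether a non-serious event enters the adverse event data. The schedule places two thyroid panels between the 30-day and the 135-day limits.

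Two texts in the same appendix then give different answers. By the general statement, an immune-mediated hypothyroidism found at Week 10 is an AESI. By the list, it is not. A site that follows the list does nothing wrong, yet the safety tables would undercount endocrine toxicity. The TSH and T4 values would still be in the database, but a laboratory value carries no diagnosis, grade, relatedness or outcome.

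**Working it through.** This is calendar arithmetic, with Day 1 as the first dose. There is no design calculation to reproduce.

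**Inputs**
- Two 21-day cycles (A13-4.1.2, A14-4.1.2 for Cohort 1, A16-4.1.2), so the final dose is on Day 22, or Day 23 with the +1 day allowance.
- Surgery at Week 7 ± 7 days: Day 43 nominal, Day 36 to Day 50.
- Week 10 visit at least 20 days after surgery. Week 13 visit 6 weeks (42 days) after surgery (footnote b).
- Windows of 30 and 135 days after the final dose (footnote f).

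**Window ends**
- All adverse events: 22 + 30 = Day 52 (Day 53 with +1 day).
- SAEs and AESIs: 22 + 135 = Day 157 (Day 158 with +1 day).

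**Thyroid panels in a patient who has surgery**

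| Surgery | Week 10, earliest (+20) | Week 13 (+42) | 6 months (+183, assumed) |
|---|---|---|---|
| Day 36 | Day 56 | Day 78 | Day 219 |
| Day 43 | Day 63 | Day 85 | Day 226 |
| Day 50 | Day 70 | Day 92 | Day 233 |

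The Week 10 and Week 13 panels fall after Day 52 and before Day 157 in every row. The 6-month panel falls after both limits.

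**Could a delayed Cycle 2 bring the visits back inside 30 days?** Week 10 is inside only if surgery comes at most 30 − 20 = 10 days after the final dose. With surgery on Day 36 that needs a Cycle 2 delay of at least 36 − 22 − 10 = 4 days. With surgery on Day 43 it needs at least 43 − 22 − 10 = 11 days. Week 13 cannot be inside, because 42 days after surgery already exceeds 30.

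**One dose only.** The ordinary window then closes on 1 + 30 = Day 31. With surgery on Day 43, the pre-surgery visit (at most 8 days before) is on Day 35 or later, so the Week 6 panel is also outside.

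**Who is not affected**
- Patients without surgery: the discontinuation visit is at most 30 days after the final dose (footnote b).
- Cohort 2 (Table A14-6): there is no Week 10 or Week 13 visit, testing is every 3 cycles on treatment, and the discontinuation visit is within 30 days.
- Week 6 cases after two doses on schedule, events whose onset is dated within 30 days, serious cases, and thyroid failure reported as hypophysitis.

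**The case against.** The best defence is that the general statement already makes every immune-mediated event an AESI, so hypothyroidism would be collected to 135 days whatever the list says. A reader might infer from the list that late hypothyroidism is certain to go unreported. The documents do not support that, because the two texts conflict and neither is given precedence. What remains is that a site using the list, which the general statement itself cites, would not report the case.

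It can also be said that the list is selective on purpose. The wording about specified events in A14-5.1.1.3 and A16-5.1.1.3 points that way, and hypothyroidism is named as a risk only for atezolizumab, which is not given in the A14 and A16 arms. Those appendices refer only to endocrinopathies or endocrine organs. This weakens the named-risk argument in two arms. It does not explain why hyperthyroidism is listed and hypothyroidism is not, and it leaves A14 and A16 with two different rules.

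A third point is that Sections 5.2.3, 5.4.2 and 5.6, which the appendices cite, lie outside the text reviewed here and might contain a further provision. The one extra non-serious category that footnote f attributes to Section 5.6 is events that delay surgery. It cannot cover an event first found after surgery.

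Finally, the thyroid values are collected in any case. That is true, and it limits the harm to the adverse event record.

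**Conclusion.** The inconsistency is real and minor. The endocrine entry in three AESI lists conflicts with the statement that immune-mediated adverse events are AESIs and, in A13, with a named risk. If sites apply the list, a non-serious hypothyroidism with onset after Day 52 in a Cohort 1 surgical patient is not reported from the Week 10 or Week 13 panel, while hyperthyroidism at the same visit is.

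This rests on a final dose on Day 22, surgery within its window, no new systemic anti-cancer therapy before the visit, and no overriding rule in the sections not reviewed.

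Two larger claims might be inferred and are not supported. One is a stated size of undercount: the documents give no incidence of hypothyroidism. The other is a proven bias between arms: the omission is identical in the three tiragolumab lists, and the control-arm list was not available. The RO7247669 monotherapy lists (A12-5.2, A15-5.2) do differ. They name no immune-mediated event at all, although A12-5.1.1.3 and A15-5.1.1.3 say that specified ones are AESIs.

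**What to change.** Add hypothyroidism to the endocrine entry in A13-5.2, A14-5.2 and A16-5.2. The lists then agree with the general statement on this event, and cases are collected to 135 days or until new systemic anti-cancer therapy starts. Align the wording in A14-5.1.1.3 and A16-5.1.1.3 with A14-5.1.2.3 and A16-5.1.2.3, so that each appendix has one rule.

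To keep ascertainment alike across arms, reconcile A12-5.2 and A15-5.2 with A12-5.1.1.3 and A15-5.1.1.3 at the same time, and check the control-arm list. Changing only the tiragolumab lists would add a difference in collection against the monotherapy arms.

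If the omission is deliberate, narrow the general statements in A13-5.1.2.3, A14-5.1.2.3 and A16-5.1.2.3 instead, and note in the safety reporting that non-serious hypothyroidism is collected only to 30 days.

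The cost is one word in each of three lists, the related edits, and some additional 24-hour reports of events expected to be mostly low grade. The panel 6 months after surgery (about Day 219 to 233) stays outside the reporting window even after the change.
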